Our central hypothesis is that our LIFT (+/- REAP) intervention will 1) improve adherence to recommended levels of exercise in end-stage liver disease 2) reduce pre-transplant frailty and 3) will improve pre- and post-transplant clinical outcomes.

STUDY ENDPOINTS:

Primary endpoints:

- Frailty (measured by Liver frailty index [LFI])
- Clinical outcomes: placement on LT waitlist, waitlist-mortality, post-transplant mortality, post-transplant disposition (acute rehabilitation, subacute rehabilitation center, home, etc), number of hospitalizations, duration of hospitalizations, liver related complications (ascites, hepatic encephalopathy, variceal bleeding, hepatorenal syndrome, hepatopulmonary syndrome, infections).
- Feasibility (measured by 8-question emailed survey)

[figure not shown]
Secondary endpoints:

- Endurance (measured by the 4-meter walk test).
- Patient adherence to the home exercise prescription (measured by daily diary counts of adherence to prescribed exercises, tracked on the TrueCoach application)
- Degree of hepatic encephalopathy (measured by List Sort Working Memory [LSWM] test and the Flanker Inhibitory Control and Attention [FICA])
- Patient-reported quality of life (measured by various PROMIS questionnaires)
- Feasibility/acceptability (measured by a study-specific questionnaire evaluating the acceptability and feasibility as reported by patients, providers and support staff)

STUDY INTERVENTION(S) / INVESTIGATIONAL AGENT(S):

Home exercise prescription (HEP) detailed below in study design.

PROCEDURES INVOLVED:

Recruitment for Quality of Life Assessment Study:

- A Northwestern Medicine Enterprise Data Warehouse (NMEDW) search will be used to identify all patients who have been seen in Transplant Evaluation Clinic and are currently being considered for liver transplantation or are already on the waitlist or have received a transplant.
- Alternatively, a list of the patients described above will be obtained from the transplant coordinator.

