- Patients will be called directly to introduce the study (script attached). A treatment relationship already exists with these patients, making an opt out letter unnecessary. If patients are interested in participating, consent will be obtained verbally. This verbal consent form is attached to the study submission. The consent form will be reviewed over the phone. Patients or their POA will provide their consent verbally, and the study team will document in the study records. A copy of this consent form will be mailed to each patient.

Recruitment for PT Intervention Study

- The Hepatology Clinic (Tuesday AM) schedule and the Transplant Evaluation Clinic (Thursday AM) schedule will be used to identify patients who are scheduled to be seen in clinic within 1 month. On a weekly basis, patients will be called directly to introduce the study (script attached). A treatment relationship already exists with these patients, making a recruitment letter unnecessary. If patients are interested in participating, consent will be obtained electronically. This consent form will be the same as the written consent form (attached). The link to this document will be emailed or texted to patients. The consent form will be reviewed over the phone. Patients or their POA will provide their e-signature and the date of consent, which will be acquired via REDCap. A copy of this consent form will be e-mailed to each patient.
- If unable to contact patients prior to their scheduled appointment, recruitment will also take place in Hepatology Clinic and Transplant Evaluation Clinic. In this case, informed consent will be obtained from patients or their present POA on an Ipad (via REDCap) before any research activities (attached).
- Patients will also be recruited if admitted to Northwestern Memorial Hospital and identified as transplant candidates or undergoing an expedited transplant evaluation. Consent will be obtained in person using an Ipad as documented above.

All participants who enroll in the PT intervention study -

Baseline session:

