- Baseline clinical data will be collected at time of enrollment via the NMEDW and via chart review (will submit EDW exception). Data will include: Age, gender, race, ethnicity, body mass index (BMI), employment status, education, marital status, etiology of liver disease, complications of liver disease (ascites, hepatic encephalopathy, presence of esophageal/gastric varices, history of variceal bleeding, hepatorenal syndrome, hepatopulmonary syndrome), medical history (coronary artery disease, chronic kidney disease, dialysis dependence, hypertension, hyperlipidemia), and baseline laboratory data (platelets, serum sodium, serum creatinine, PT/INR, total bilirubin, albumin, calculated MELD) (Appendix A, B)
- Components of baseline session: (1) personality assessment (2) patient-reported quality of life assessment (3) hepatic encephalopathy assessment (4) frailty assessment, (5) physical therapy introduction.

- Personality assessment
 - Setting:
 - If consented over the phone prior to clinic visit, the personality survey will be emailed/texted to patients and completed over the telephone with a team member.
 - If consented in clinic visit or while admitted inpatient, the personality survey will be completed in clinic or at bedside with a team member.
 - Tool: Modified Midlife Development Inventory (MIDI) Personality Scale
 - Time: 38 questions, 3-5 minutes
 - Data collected via REDcap
 - Appendix C
- Patient-reported quality of life assessment (in clinic)
 - Setting:
 - If consented over the phone prior to clinic visit, the QOL survey will be emailed/texted to patients and completed over the telephone with a team member.
 - If consented in clinic visit or while admitted inpatient, the QOL survey will be completed in clinic or at bedside with a team member.
 - Tools: PROMIS surveys: Physical function – Short form 8c, Cognitive Function
 - Time: ~15 questions, 5 minutes
 - Data collected via REDcap
 - Appendix D
- Hepatic encephalopathy assessment
 - Setting: in clinic or at bedside if inpatient.
 - Tools: List Sort Working Memory (LSWM) test, the Flanker Inhibitory Control and Attention (FICA) test, Pattern Comparison Processing Speed Test administered on ipad and keyboard.
 - Time: 16 minutes (LSWM – 7 minutes, FICA – 3 minutes, PCPS – 3 minutes)
 - Appendix E
- Frailty assessment
 - Setting: in clinic or at bedside if inpatient.
 - Tools: Liver Frailty Index, 4-meter walk test
 - Balance testing
 - Repeat chair stands
 - Grip testing

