 - Number of hospitalizations, intensive care unit admissions, duration of hospitalizations, duration of intensive care unit admission, development of decompensating events (ascites, hepatic encephalopathy, presence of esophageal/gastric varices, history of variceal bleeding, hepatorenal syndrome, hepatopulmonary syndrome, infections), transplant status, date of death, cause of death, placement on LT waitlist, delisting from LT waitlist, date of transplant, type of LT (living donor LT, simultaneous liver-kidney), duration of hospital admission for LT, duration of ICU admission for LT, duration of intubation post-LT, post-transplant discharge disposition, post-transplant complications (rejection, infection, biliary complications, hypertension, hyperlipidemia), liver frailty index scores, Karnofsky Performance Status Scores, body mass index (BMI), and laboratory data (platelets, serum sodium, serum creatinine, PT/INR, total bilirubin, albumin, calculated MELD).

DATA AND SPECIMEN BANKING

Data/specimens will not be banked for future use.

The data collected in this study will also be used in the Functional Assessment in Liver Transplantation study (STU00203582), The Role of Circadian Dysfunction in Hepatic Encephalopathy in Patients with Cirrhosis study (STU00204423), and the Personality, QOL and Frailty in Liver Transplantation study (STU00212668).

SHARING RESULTS WITH PARTICIPANTS

Study results will not be shared with participants or anyone else.

STUDY TIMELINES

Patients will be prospectively enrolled in the study from 9/13/2020 vs date of IRB approval to 7/31/2025. Patients in the Quality of Life Assessment arm will remain enrolled in the study while on the liver transplant waitlist and until 3 years after liver transplantation or up to a maximum of 5 years if not listed for liver transplantation. Patients in the PT Intervention arm will remain enrolled in the study while on the liver transplant waitlist and until 1 year after liver transplantation or up to a maximum of 5 years if not listed for liver transplantation. The estimated date for completion of primary analyses is 9/1/2025.

INCLUSION AND EXCLUSION CRITERIA

PT Intervention Study

Inclusion (criteria will be confirmed during consent process and during in-clinic physical therapy evaluation)

- Patients with a diagnosis of liver cirrhosis being evaluated for liver transplantation in hepatology/transplant evaluation clinic
- English-speaking

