- If unable to contact patients prior to their scheduled appointment, recruitment will also take place in Hepatology Clinic and Transplant Evaluation Clinic. In this case, informed consent will be obtained on an Ipad (via RedCAP) from patients or their present POA before any research activities (attached).
- Patients will also be recruited if admitted to Northwestern Memorial Hospital and identified as transplant candidates or undergoing an expedited transplant evaluation. Consent will be obtained in person using an Ipad as documented above.

COMPENSATION FOR PARTICIPATION IN RESEARCH ACTIVITIES

Participants will not be compensated for their participation in this study.

WITHDRAWAL OF PARTICIPANTS

Patients will not be withdrawn from the study unless they request withdrawal themselves or if it is determined that it is in the best interest of patients' health and welfare to stop. Patients who are cognitively impaired will be withdrawn from the study if they appear unduly distressed.

RISKS TO PARTICIPANTS

PT Intervention Study:

Falls or muscle strains while exercising at home and during the measurement of liver frailty index are a risk involved in the study.

- This risk will be minimized by the presence of trained physical therapists during LFI testing in clinic.
- Detailed instructions on exercise plans will be provided to minimize the risk of falls at home. Potential concerns regarding exercises will be addressed during weekly calls with the research team. Physical therapists will be available to speak with patients about exercises throughout the study course.
- The exercises recommended for study participants will be similar to the exercises recommended to all patients being evaluated for liver transplantation, regardless of study participation. This is part of the standard of care and is thus, not a significant risk of the study itself.

PT Intervention Study and QOL Assessment Study:

A confidentiality breach is a risk associated with data review research. All necessary precautions will be done to prevent a confidentiality breach as per FSM data security policy.

- All electronic versions of data sets will be kept in password protected computers on a password protected server with access only to the project investigators and project staff. Subjects' names will be kept in a separate file from any findings by using a unique study code number for each participant.

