 - Ability to provide consent will be assessed by the research team member introducing the research study and obtaining consent. Patients' capacity to consent will be assessed by asking the patients to clearly state the purpose of the study and what the study entails. They will be asked to outline the potential benefits and consequences of the study. They will be assessed on their understanding that the study is voluntary and their understanding that deciding not to participate will not impact their medical care negatively in any way.
 - If a participant is unable to provide consent, consent will be obtained from the participant's durable power of attorney for health care, court appointed guardian for health care decisions, spouse, and adult child, in this order.
 - If a patient is determined to not have capacity to provide consent, the research study will still be explained to the patient in a level suitable to their understanding.
- *Process to Document Consent in Writing*

PT Intervention participants

Please see Written Consent Form attached. This is the separate consent form for the LIFT+/- REAP study.

QOL Assessment participants

Please see the Verbal Consent form. This is the separate consent form for the QOL assessment study.

The researchers request a waiver of written consent for the QOL assessment study participants. The verbal consent form contains all elements of consent disclosure, and the QOL assessments are minimal risk. Interventions are limited to surveys and an EDW query of their medical records. These interventions would not require consent in a standard clinical context.

Moreover, the researchers have found that eConsent has not been practicable for the study population, which is generally elderly, chronically ill, and not technically savvy. As such, the researchers estimate that 30% of study candidates have been lost due to technical difficulties with the eConsent process.

PROTECTED HEALTH INFORMATION (PHI AND HIPAA)

- This study does involve the creation and use of PHI.
- HIPAA authorization will be obtained from all patients seen in Hepatology and Transplantation Evaluation Clinic, the setting in which participants are recruited.
- Specific PHI to be obtained from the EDW and chart review are outlined in Appendix A, B.
- QOL Assessment participants

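### PT eligibility is written for clinic patients, but inpatients are also recruited with a bedside baseline LFI, and the plan does not account for recruitment setting

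*Combined protocol and SAP*

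**What the plan says.** Two sets of passages describe who enters the PT Intervention Study.

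**Clinic only.** Under INCLUSION AND EXCLUSION CRITERIA, the study takes "Patients with a diagnosis of liver cirrhosis being evaluated for liver transplantation in hepatology/transplant evaluation clinic", and the "criteria will be confirmed during consent process and during in-clinic physical therapy evaluation". CONSENT PROCESS names the clinics as the place of enrolment, alongside an online consent form. PROTECTED HEALTH INFORMATION states: "HIPAA authorization will be obtained from all patients seen in Hepatology and Transplantation Evaluation Clinic, the setting in which participants are recruited".

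**Clinic and ward.** PROCEDURES INVOLVED and RECRUITMENT METHODS both say: "Patients will also be recruited if admitted to Northwestern Memorial Hospital and identified as transplant candidates or undergoing an expedited transplant evaluation". The baseline session follows suit. For the encephalopathy, frailty and physical therapy components it gives "Setting: in clinic or at bedside if inpatient".

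LFI is a primary endpoint. After baseline it is measured at home by video every 4 weeks, and in clinic every 3 months. Randomisation is 1:1 at 2 weeks after the baseline session, with no stratification factor named. The Statistical analysis section specifies t-tests and chi-squared tests between LIFT and LIFT + REAP. The comparator without LIFT is a retrospective group evaluated for transplantation at the same hospital from January 2018 to October 2020.

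**The concern.** Site staff cannot tell from the text whether enrolling a patient evaluated only in hospital is permitted or is a protocol deviation.

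The measurement question matters more. For an inpatient, the only baseline LFI is taken during an admission, and the next scheduled one is at home 4 weeks later. No section repeats LFI after discharge or at randomisation. A change in LFI over that interval may reflect the course of the acute illness as well as the exercise programme.

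Aim 2 and the second part of the central hypothesis concern the effect of LIFT, with or without REAP, on frailty. Both randomised arms receive LIFT, so LIFT itself can be judged only by change from baseline or against the retrospective group. Those are the readings in which setting can be confounded with treatment.

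Two counting rules are also missing. Number and duration of hospitalisations are primary endpoints, and the plan does not say whether an admission already under way at enrolment counts. Adherence is a daily count of home exercises, and the plan does not say how days in hospital are treated.

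**Working it through.** **1. The passages side by side.** A patient already under evaluation in clinic who is then admitted can satisfy both the inclusion criterion and the inpatient recruitment rule. A patient whose evaluation takes place only in hospital, such as an expedited case, satisfies the recruitment rule but not the criterion. That patient also has no in-clinic visit before enrolment at which eligibility could be confirmed. The conflict is therefore real but limited to the second kind of patient.

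**2. The plan's own figure.** The sample size of 500 cannot be reproduced: it covers all groups, and no alpha, power, effect size, SD or dropout is given. For scale only, suppose all 500 were PT patients (250 per arm), with an assumed two-sided alpha of 0.05. The detectable difference is (1.960 + 0.842) × √(2/250) = 0.25 SD at 80% power and (1.960 + 1.282) × √(2/250) = 0.29 SD at 90%.

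**3. Before-after reading.** Let f be the inpatient share and r the mean improvement in inpatients' LFI without any treatment effect, in SDs of change within a setting. Both are assumptions.

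- Spurious mean change = f × r. Examples: 0.05 × 0.5 = 0.025 SD; 0.20 × 0.5 = 0.10 SD; 0.30 × 1.0 = 0.30 SD.
- If inpatients deteriorate instead, r is negative and the product changes sign.
- Hand check for f = 0.20, r = 0.5, N = 500. The variance of change is 1 + r²f(1 − f) = 1 + 0.25 × 0.16 = 1.04. The expected z is 0.10 × √500 / √1.04 = 2.19. The chance of p < 0.05 is about Φ(2.19 − 1.96) = 0.59.

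**4. Simulation.** There were 4,000 runs per row, with no true treatment effect and 1:1 allocation. The before-after test is a one-sample t-test of change; the between-arm test is a two-sample t-test.

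| N | f | r | Mean improvement (SD) | False positive, before-after | False positive, between arms |
|---|---|---|---|---|---|
| 500 | 5% | 0.5 | 0.025 | 8.3% | 5.0% |
| 500 | 20% | 0.5 | 0.10 | 59.0% | 5.2% |
| 500 | 30% | 1.0 | 0.30 | 100% | 5.0% |
| 100 | 5% | 0.5 | 0.025 | 6.7% | 4.4% |
| 100 | 20% | 0.5 | 0.10 | 16.6% | 5.1% |
| 100 | 30% | 1.0 | 0.30 | 77.4% | 5.1% |

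Over all combinations run (f from 5% to 30%; r of 0.5 or 1.0; N of 100 or 500), the between-arm false-positive rate stayed between 4.4% and 5.4%.

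**5. What setting does to the randomised comparison.** The expected difference is f × r − f × r = 0.

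- Variance of change is multiplied by 1 + r²f(1 − f): 1.04 for f = 0.20, r = 0.5, and 1 + 1 × 0.21 = 1.21 for f = 0.30, r = 1.0.
- The SD of the chance difference in inpatient share is √(2f(1 − f)/n). With f = 0.20 and n = 250 per arm this is √(0.32/250) = 0.036, which moves the LFI contrast by 0.036 × 0.5 = 0.018 SD. With n = 50 per arm it is √(0.32/50) = 0.08, or 0.04 SD.

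**The case against.** The strongest reply is that the only between-group comparison specified is LIFT against LIFT + REAP, randomised after baseline. A reader might infer that bedside baselines bias that comparison. They do not: change after admission is balanced in expectation, and the simulation agrees. No before-after test and no test against the retrospective group is written. This stands, and it confines the bias to readings that Aim 2 invites but the analysis section does not specify.

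Other strong readings also go beyond the documents:

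- *Every inpatient is ineligible.* A patient under clinic evaluation who is admitted can meet the criterion. The bedside provisions show that the inpatient route is deliberate, so the eligibility wording may simply not have been aligned with it.
- *The comparator was measured in clinic.* The retrospective group is everyone evaluated at the hospital, with no restriction on setting. Frailty testing is said to be done in all clinic patients, but the source of the controls' scores is not stated, and their inpatient mix could be similar.
- *Recovery makes LIFT look effective.* The documents give no reason for admission and no LFI course. Expedited patients might worsen, or be transplanted before the 4-week measurement.
- *The index admission inflates the hospitalisation endpoints, and hospital days lower adherence.* Neither rule is written. The gap is a missing definition, not a wrong one.

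The objection does not remove the conflict between sections, or the absence of any provision for setting.

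**Conclusion.** The concern holds in a limited form. The eligibility, consent and HIPAA sections describe a clinic population, whereas the recruitment and baseline sections also provide for inpatients. Patients evaluated only in hospital fall outside the criterion as written.

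The randomised comparison remains valid. Under the assumptions shown, its cost from ignoring setting is modest: 4% more variance in the middle case and 21% in the most extreme. Chance imbalance is typically 0.018 to 0.04 SD at 20% inpatients and r = 0.5.

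A before-after reading of LIFT could carry a spurious mean change of 0.025 to 0.30 SD in either direction. A historical-control reading could be affected if the setting mix differs. These figures rest wholly on assumed inpatient shares and LFI changes. Only the textual conflict and the missing provisions are established by the documents.

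**What to change.** Reconcile the inclusion criteria, CONSENT PROCESS and PROTECTED HEALTH INFORMATION with PROCEDURES INVOLVED, the baseline session and RECRUITMENT METHODS, so that eligibility states whether inpatients are admitted and where their criteria are confirmed. If they are admitted:

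1. Record recruitment setting (inpatient or clinic) at enrolment and stratify the 1:1 randomisation by it.
2. Adjust the LFI comparison for setting and baseline LFI, for example with a linear model in place of the unadjusted t-test.
3. Count only admissions that begin after enrolment in the number and duration of hospitalisations.
4. Leave hospital days out of the denominator for home-exercise adherence.
5. For any before-after or historical-control reading of LFI, report a sensitivity analysis in patients with a clinic baseline, and match or adjust for setting against the retrospective group.

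The cost is one amendment, one stratification factor and slightly more analysis work.

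Closing the inpatient route, moving baseline to after discharge and delaying randomisation to discharge are not required. The last two carry their own problems. Equipment and exercise instruction are given at the bedside, so a later baseline could follow exposure to the intervention. Waiting for discharge would also lose patients who die or are transplanted first.

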 - If patients have questions regarding exercise regimen, they will be contacted by a physical therapist.
 - Progress reviewed and exercise regimen potentially adjusted by a physical therapist based on data collected and patient experience.
- *Clinical data collection via NEDW and review of EMR (every 4 weeks)*
 - Number of hospitalizations, intensive care unit admissions, duration of hospitalizations, development of decompensating events (ascites, hepatic

encephalopathy, variceal bleeding), transplant status, type of LT (living donor LT, simultaneous liver-kidney), duration of hospital admission for LT, duration of ICU admission for LT, duration of intubation post-LT, post-transplant discharge disposition, date of death, cause of death, post-transplant complications (rejection, infection, biliary complications).

- *Clinic visits (every 3 months, same tools as noted above)*
 - Patient-reported quality of life assessment
 - Hepatic encephalopathy assessment
 - Frailty assessment, 4-meter walk test (standard of care)
 - Physical therapy in person update (standard of care)
 - Data collection via NMEDW extraction and chart review: Number of hospitalizations, intensive care unit admissions, duration of hospitalizations, development of decompensating events (ascites, hepatic encephalopathy, variceal bleeding), transplant status, type of LT (living donor LT, simultaneous liver-kidney), duration of hospital admission for LT, duration of ICU admission for LT, duration of intubation post-LT, post-transplant discharge disposition, date of death, cause of death, post-transplant complications (rejection, infection, biliary complications).
- Feasibility assessment (for those who remain in the study for at least 1 month or until receiving a liver transplant; surveys emailed)
 - Tool: 8 -question survey emailed to eligible subjects as noted above.
 - Data collected via REDCap.
 - Time: < 3 minutes
 - Appendix G

All participants who enroll for the PT intervention will be randomized (1:1) into the LIFT subgroup or the LIFT + REAP subgroup at 2 weeks after enrollment/baseline session. The LIFT subgroup will continue to follow up as detailed above. The LIFT + REAP subgroup will undergo Realistic Effort Action Planning (REAP), which is described below:

LIFT + REAP subgroup:

Follow up:

- *REAP introduction (2 weeks after enrollment, via telephone/videoconference, time: 30 minutes)*
 - Performed by a member of the research team.

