- Only the principal investigator and co-investigators listed on this study will have access to harvested patient data.
- Any documents containing identifiable information will be destroyed within five years of project completion using electronic "shredding" software.

POTENTIAL BENEFITS TO PARTICIPANTS

PT Intervention Study:

Improvement in physical function (decreased frailty), which should improve pre- and post-transplantation outcomes, is the primary benefit of participating in the study. Based on the current literature demonstrating the negative impact of frailty on clinical outcomes in liver transplantation, improvement in clinical outcomes with improvement in physical function is likely.

QOL Assessment Study:

There is no direct benefit to participation.

DATA MANAGEMENT AND CONFIDENTIALITY

Only IRB approved personnel will have access to the data. All data will be stored on FSM shared drive-accessed only by approved personnel. All data is accessed through password protected computer kept in locked offices. All patient identifiers will be stored in a separate password protected file.

These data will be presented at national meetings (i.e. American Transplant Congress, etc) and a manuscript will be written for consideration of publication in respected, peer-reviewed journals (i.e. American Journal of Transplantation). All publications will include only aggregated data and no patient identifiers will ever be reported. Data will be stored until 3 years after the end of the project and will be destroyed.

QOL Assessment study

As PHI will be collected under a waiver of written HIPAA authorization, the PHI collected for these participants will not be reused or disclosed to any other person or entity, and the identifiers will be destroyed at the time of IRB closure.

Statistical analysis:

Chi-squared tests will be used to assess differences in categorical clinical endpoints and T-tests will be used to assess differences in continuous clinical endpoints between the LIFT and LIFT + REAP subgroups. Multivariate analysis will be used to assess clinical factors associated with clinical endpoints in each group. Survival analysis will be conducted after controlling for all the variables that are significant during regression analysis.

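### Chi-squared and t-tests on the clinical endpoints ignore unequal time at risk: they lose power when follow-up is similar in both arms and can mislead when it is not

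*Combined protocol and SAP*

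**What the plan says.** Statistical analysis (under Data Management and Confidentiality) gives the comparison of LIFT with LIFT + REAP in one sentence: "Chi-squared tests will be used to assess differences in categorical clinical endpoints and T-tests will be used to assess differences in continuous clinical endpoints". It adds that "Survival analysis will be conducted after controlling for all the variables that are significant during regression analysis". That second sentence names no endpoint, time origin, censoring rule or competing event.

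Study Endpoints lists the clinical outcomes among the primary endpoints. They include "placement on LT waitlist, waitlist-mortality, post-transplant mortality, post-transplant disposition" and the number and duration of hospitalizations. No assessment window or per-person-time definition is attached to any of them.

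Study Timelines sets accrual: "Patients will be prospectively enrolled in the study from 9/13/2020 vs date of IRB approval to 7/31/2025". PT Intervention participants stay in the study while on the waitlist and "until 1 year after liver transplantation or up to a maximum of 5 years if not listed for liver transplantation". It also states: "The estimated date for completion of primary analyses is 9/1/2025".

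Procedures Involved says that participants "will be randomized (1:1) into the LIFT subgroup or the LIFT + REAP subgroup at 2 weeks after enrollment/baseline session".

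**The concern.** The planned tests treat every participant as if observed for the same length of time. Here one patient may contribute a few weeks and another several years. A raw admission count mixes how often a patient is admitted with how long the patient was watched. A raw proportion of waitlist deaths mixes the death hazard with the speed at which transplant removes patients from waitlist risk.

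Two things are at stake. Variation in follow-up adds noise, so real differences are harder to detect. And if LIFT + REAP changes time to listing, transplant, death or dropout, which is close to the trial's own hypothesis of better pre- and post-transplant outcomes, the arms will have different time at risk. A difference or null result could then reflect exposure, not the admission rate or the death hazard.

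A separate problem concerns post-transplant mortality and disposition. They are defined only in patients who reach transplant, a group formed after randomization that the intervention may itself alter.

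**Working it through.** **1. Range of follow-up (dates from Study Timelines).**
- Shortest: 7/31/2025 to 9/1/2025 = 32 days from enrolment. Randomization is 2 weeks later, so 32 − 14 = 18 days from randomization.
- Longest: 9/13/2020 to 9/1/2025 = 1,814 days (4.97 years). It is shorter if IRB approval came after 9/13/2020.
- Ratio: 1,814 / 32 ≈ 57.
- Accrual spans at most 1,782 days, of which 333 fall after 9/1/2024. If accrual is uniform (an assumption), 333 / 1,782 = 18.7% of participants cannot have a full year of post-transplant follow-up by 9/1/2025. Administrative censoring will therefore be common.

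**2. What each test compares.** Let X be a patient's time at risk and λ the admission rate.
- The mean raw count in an arm is λ × E[X]. The t-test therefore compares λ₁E[X₁] with λ₀E[X₀], which is a comparison of rates only if E[X₁] = E[X₀]. Even then, the variation in X inflates the variance.
- With constant death hazard d, transplant hazard t and potential follow-up c, the probability of waitlist death is d/(d + t) × (1 − exp(−(d + t)c)). It falls as t rises, with d unchanged.
- Example by simulation (assumed d = 0.3 per year in both arms; t = 0.8 versus 0.8 × 1.3 = 1.04 per year; uniform accrual): 22.5% versus 19.2% die on the waitlist. With an admission rate of 1.5 per year in both arms, mean pre-transplant counts are 1.125 versus 0.958.

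**3. Simulation at 250 per arm.** None of these inputs is in the documents: waitlist death 0.15 to 0.30 per year, transplant 0.4 to 0.8 per year, 1.5 admissions per year before transplant with gamma frailty of variance 1, uniform accrual, 3,000 runs, two-sided 5%. The comparators are a log-rank test censored at transplant and a person-time rate ratio with robust variance.
- No effect, equal transplant rates: chi-squared rejects 4.7–5.1%, t-test 4.9–5.6%, log-rank 4.4–4.9%, rate ratio 5.4–6.1%.
- Death hazard ratio 0.6 and admission rate ratio 0.75, equal transplant rates: power is 54–73% (chi-squared) versus 58–82% (log-rank), and 18–30% (t-test) versus 49–58% (rate ratio).
- No effect on death or admission rates, but faster transplant in one arm. At transplant hazard ratio 1.3, chi-squared rejects 9–15% and the t-test 11–15%. At 1.5 they reject 17–29% and 18–30%. Log-rank stays at 4.2–4.9% and the rate ratio at 5.1–6.1%.
- At 100 per arm, the last scenario gives 7–14% (chi-squared) and 7–15% (t-test).

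**4. Hospitalization counts with and without the post-transplant year.** Assumed: 1 admission per year, gamma shape 1, uniform accrual, 100 per arm unless stated.
- True 35% reduction, equal exit: t-test power 36% versus 51% for a rate model if counting stops at exit; 45% versus 58% if counting continues for 1 year after transplant.
- Equal admission rates, exit rates of 0.7 versus 0.4 per year: the t-test rejects about 24% if counting stops at exit. If 0.7 and 0.4 are transplant rates and 1 further year is counted, it rejects about 7% at 100 per arm and 12% at 250 per arm. These last figures move by a few percentage points with the assumed death rate.
- Milder contrast, counting stopped at exit: 0.6 versus 0.5 per year gives about 7%.

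**5. The survival sentence.** It cannot handle admission counts or days. For mortality it is not said to replace the chi-squared test, and its covariates are chosen by significance in an earlier regression.

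**The case against.** The strongest reply is that under 1:1 randomization, with the same follow-up pattern in both arms, the planned tests are valid. That stands: step 3 shows type I error near 5%. A reader might infer from the wide follow-up range that the tests are simply wrong; the documents do not support that. Both arms receive the same LIFT programme and differ only by REAP, so a large contrast in exit is possible but not shown.

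A reader might also infer that follow-up ends at transplant. It does not. Only waitlist time at risk ends there; study follow-up runs for a further year, and the hospitalization endpoint is not confined to the pre-transplant period. The 24% rejection rate depends on stopping the count at exit and on a large assumed contrast, so it should not be read as the expected error.

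Nor can it be said that time-to-event analysis is absent. One is named, and for mortality the fault is that it is unspecified. Even with unequal transplant timing, chi-squared reflects a real difference in the proportion dying on the waitlist; it is just not a difference in hazard.

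That nobody can reach 5 years by 9/1/2025 is not a defect either. Five years is a cap, and the analysis date is described as estimated.

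Finally, the remedy has limits. A rate model assumes that exit is not strongly related to a patient's own admission rate. In a simulation where sicker patients exited faster (0.7 versus 0.4 per year), a person-time rate ratio also over-rejected, at about 10%. A fixed window or a recurrent-event model that includes death would be defensible alternatives.

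What remains is that the plan states a method that performs worse on primary endpoints, and nothing else in the documents makes up for it.

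**Conclusion.** The point holds in a conditional form. Follow-up of 32 to at most 1,814 days is date arithmetic from the protocol, and no window, offset, cut-off, censoring rule or competing-event rule is given. With similar follow-up in both arms the consequence is lost power, modest for chi-squared on mortality and larger for the t-test on admissions (36–45% against 51–58% in step 4). With follow-up that differs by arm, the tests can reject well above 5% as tests of rate or hazard. The size depends on the assumed exit pattern, from about 7% to about 30% across the scenarios shown. All simulated figures rest on assumed rates and arm sizes; the protocol gives only a total of 500 across all groups. They show direction and range, not a forecast.

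The post-transplant point needs no simulation: a comparison restricted to transplanted patients is not a randomized comparison.

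The documents call this a pilot and the tests are not invalid in general, so this is something that should be fixed, not a flaw that defeats the trial.

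**What to change.** In Statistical analysis, set the time origin at randomization and state a data cut-off date with administrative censoring. Then:

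1. Analyse number and days of hospitalization by a count model with a log person-time offset (for example negative binomial with robust variance), and add a sensitivity analysis that treats death as a terminal event.
2. Analyse waitlist death by cumulative incidence and cause-specific hazard, with transplant as a competing event, in place of chi-squared.
3. Test all-cause death in all randomized patients irrespective of transplant. Report post-transplant mortality and disposition as descriptive, conditional on transplant, with the number transplanted in each arm.
4. Fix the adjustment covariates in advance instead of selecting them by significance.

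The cost is SAP wording and a little more analysis work. Transplant status and date of death are already collected every 4 weeks for PT participants. Listing and transplant dates are itemised for the Quality of Life and retrospective control groups but not in the PT follow-up list; they would be taken from the medical record. The rate model's assumption about exit should be stated. Moving the clinical-outcome analysis to a later date would add post-transplant follow-up but is optional.
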